#### 9.4.2 Design Considerations following December 2017 and 2018 DSMB Reviews

In follow-up to their December 2017 review, the REPRIEVE (A5332) DSMB recommended the following actions: 1) to cease study enrollment of patients with 10-year ASCVD risk score less than 2.5%; 2) increase study sample size by approximately 1,000 participants of higher risk population; and 3) increase the follow-up by 1 year now and consider re-evaluation of an additional follow-up extension in the future [implemented following the December 2018 DSMB Review]. These recommendations respond to the higher than anticipated enrollment of participants with very low risk and ensure that REPRIEVE (A5332) will maintain power to detect the targeted effect of interest under a broader range of scenarios for the rate of MACE in the absence of a pitavastatin (control rate). **Specifically, a total of 288 primary MACE endpoints are needed to ensure that the study will have 85% power to detect a hazard ratio of 0.7.**

#### 9.4.3 Power Considerations for non-MACE Clinical Endpoints

Since the composite rate of serious non-MACE of interest (see [section 9.2.2.4](#)) in the absence of statin is expected to exceed the rate of MACE, REPRIEVE (A5332) will be well powered to detect statin effectiveness equating to a 25% reduction in non-MACE or higher.

If the incidence of any specific class of non-MACE in the absence of statin therapy is 5/1000 PY or higher, REPRIEVE (A5332) will have 90% power to detect a statin effect equating to a 50% reduction in the non-MACE event rate or higher. Published data from the ALLRT cohort [Overton 2013] suggest that the incidence of each of these events of interest will exceed this 5/1000 PY threshold.

#### 9.4.4 Power Considerations for COVID-19 Objectives

In March 2020, when SARS-CoV-2 infections and COVID-19 diagnoses were emerging in REPRIEVE enrollment areas, approximately 6650 REPRIEVE participants remained in follow-up.

It was hypothesized that 30% of REPRIEVE participants will be antibody positive for exposure to SARS-CoV-2. This rate is considered a conservative estimate based on widespread successful implementation of mitigation strategies. Recent studies from NYC and other large US urban areas indicate infection rates of up to 30%, and this is anticipated to increase further, especially in less-developed Global Burden of Disease regions that recruited into REPRIEVE. With the use of comprehensive sensitive and specific state of the art antibody testing, as proposed in this supplement, we will be well-poised to capture a significant number of cases, independent of any differences in more localized testing rates.

Allowing for 5% additional losses to follow-up, this will yield approximately 2000 cases and 4650 controls for analyses, including about 200 hospitalizations (10% of infections, ie, serious disease), and will provide ample numbers for the proposed epidemiology, pathobiology, genetic, and clinical investigations (see [Table 9.4.4-1](#)). For example, with this rate of antibody positivity, we will be able to estimate infection risk with a precision of at least  $\pm 1.2\%$ , and will have 90% power to show a 12% reduction in the infection risk in the pitavastatin group ( $RR=0.88$ , 30% risk in the placebo group compared to 26% risk in the pitavastatin group), and 80% power to detect a 35% relative risk reduction ( $RR=0.65$ ) in serious disease (see table cells in blue font). Detectable effect sizes for antibody positivity rates of 15%-30% and power of 80%-90% are shown in the table below.

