**Table 9.4.4-1: Detectable Effect Sizes for Antibody Positivity Rates of 15%-30% and Power of 80%-90%**

Power		Proportion of Participants COVID-19 Antibody Positive (Control)			
		30%	20%	15%	
Precision to estimate infection risk	-	$\pm 0.012\%$	$\pm 0.0135\%$	$\pm 0.015\%$	
Detectable risk reduction with given power	90%	12% ( $RR=0.88$ )	15% ( $RR=0.85$ )	18% ( $RR=0.82$ )	
	85%	11% ( $RR=0.89$ )	14% ( $RR=0.86$ )	17% ( $RR=0.83$ )	
	80%	10% ( $RR=0.90$ )	13% ( $RR=0.87$ )	16% ( $RR=0.84$ )	
		Proportion of COVID-19 antibody positives experiencing serious disease			
		10%	20%	10%	20%

Detectable risk reduction with given power	90%	40% (0.60)	29% (0.71)	48% (0.52)	35% (0.65)	55% (0.45)	40% (0.60)
	85%	38% (0.62)	27% (0.73)	45% (0.55)	33% (0.67)	51% (0.49)	38% (0.62)
	80%	35% (0.65)	25% (0.75)	43% (0.57)	31% (0.69)	48% (0.52)	35% (0.65)

*\* Assumes sample size of 6650 with evaluable COVID-19 antibody results equally distributed between pitavastatin and placebo groups (see text for rationale for this number).*

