## 9.6 Analyses

### 9.6.1 General Analysis Considerations

The following sections provide a brief overview of the analysis considerations for REPRIEVE (A5332). Prior to the start of enrollment, a detailed Statistical Analysis Plan fully delineates all planned statistical analyses. **In the event of a DSMB recommendation to stop the trial for efficacy at interim review, full analysis and publication of the primary trial results will be prepared based on the frozen data for the DSMB meeting. Subsequent analyses (including a database prepared for future data-sharing requests) will be performed based on the final trial database including all final study termination visits. In the event of a DSMB recommendation to stop for futility, full analysis and publication of the primary trial results will be performed based on the final trial database including all final study termination visits.**

All major treatment comparisons between the randomized groups will be performed according to the principle of "intention-to-treat;" that is, participants will be analyzed (and endpoints attributed) according to the randomized treatment assigned regardless of subsequent changes to that treatment; as-treated analyses will also be performed. Descriptive summaries of the distribution of continuous baseline variables will be presented in terms of percentiles (eg, median, 25th and 75th percentiles), while discrete variables will be summarized in terms of frequencies and percentages. Statistical comparisons will be performed using two-sided significance tests with a 5% Type I error.

Unless otherwise noted, comparison of time to event outcomes will use methods for competing risks, notably Cox proportional hazards models for estimation of cause-specific hazard ratios and Gray's test for comparison of cumulative incidence curves.

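### The COVID-19 power section says it allows for a further 5% loss, but its case and control counts and its table still rest on the full 6650

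*Protocol*

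**What the plan says.** Protocol section 9.4.4 starts from the statement that "approximately 6650 REPRIEVE participants remained in follow-up" in March 2020. It then sets the infection rate: "It was hypothesized that 30% of REPRIEVE participants will be antibody positive for exposure to SARS-CoV-2". From these it derives the numbers for analysis: "Allowing for 5% additional losses to follow-up, this will yield approximately 2000 cases and 4650 controls for analyses". Serious disease is taken as one infection in ten, which the section puts at roughly 200 hospital admissions.

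Two headline powers follow. One is 90% for a relative risk of 0.88 on infection, described as "30% risk in the placebo group compared to 26% risk in the pitavastatin group". The other is "80% power to detect a 35% relative risk reduction" in serious disease. Both are cells of Table 9.4.4-1, whose footnote reads "Assumes sample size of 6650 with evaluable COVID-19 antibody results equally distributed between pitavastatin and placebo groups" and refers back to the text for the reason behind that number.

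Section 9.4.4 gives no significance level. The general rule in section 9.6.1 is "two-sided significance tests with a 5% Type I error".

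**The concern.** The same number, 6650, appears as the headcount before the further loss and as the evaluable count after it. It cannot be both if 5% are lost in between. If the text is right that 6650 is the March 2020 headcount, the counts and powers offered for the statin effect on infection and on serious disease do not carry the allowance that the protocol says they carry. A reader using the table to judge what a null COVID-19 result rules out would credit the study with slightly more sensitivity than its own assumptions give.

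**Working it through.** **Inputs.** From section 9.4.4: 6650 in follow-up, 5% additional loss, 30% positivity, serious disease in 10% of infections, headline RRs 0.88 and 0.65. From Table 9.4.4-1: 1:1 allocation and the printed RRs. From section 9.6.1: two-sided 5%.

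**Step 1: was anything deducted?**
- 2000 + 4650 = 6650.
- 0.30 × 6650 = 1995 and 0.70 × 6650 = 4655, which round to the stated counts.
- With the loss: 6650 × 0.95 = 6317.5, giving 0.30 × 6317.5 = 1895 cases, 0.70 × 6317.5 = 4422 controls, and 10% of 1895, about 190 hospitalisations.

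The stated counts are those of the undeducted 6650.

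**Step 2: reproduce the plan's figure.** For two proportions with n per arm, p̄ = (p1 + p2)/2 and pooled variance under the null:

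power = Φ{ [ |p1 − p2|√n − 1.96 √(2p̄(1 − p̄)) ] / √(p1(1 − p1) + p2(1 − p2)) }

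Infection headline: p1 = 0.30, p2 = 0.88 × 0.30 = 0.264, p̄ = 0.282, n = 6650/2 = 3325.
- 0.036 × √3325 = 2.0759.
- √(2 × 0.282 × 0.718) = 0.6364.
- √(0.30 × 0.70 + 0.264 × 0.736) = 0.6358.
- (2.0759 − 1.96 × 0.6364)/0.6358 = 1.303, and Φ(1.303) = 90.4%.

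The stated 90% is recovered at 3325 per arm. Solving the formula for RR at each stated power, with n = 3325, agrees with every printed RR to within about 0.005. For serious disease the agreement requires testing among all randomised, with control risk = positivity × serious proportion (0.30 × 0.10 = 3% for the headline). The table was therefore built on 6650.

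**Step 3: effect of the loss alone.** With an unrounded detectable RR, the standardised effect scales with √0.95:

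power after loss ≈ Φ{ (1.96 + z)√0.95 − 1.96 }, where z is the normal quantile of the nominal power

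- 80%: z = 0.842, giving Φ(0.771) = 78.0%.
- 85%: z = 1.036, giving Φ(0.961) = 83.2%.
- 90%: z = 1.282, giving Φ(1.199) = 88.5%.

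**Step 4: the RRs as printed, using the Step 2 formula.**

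| Cell | Stated | N = 6650 | N = 6317.5 |
|---|---|---|---|
| Infection, RR 0.88 at 30% | 90% | 90.4% | 88.9% |
| Infection, RR 0.90 at 30% | 80% | 77.3% | 75.2% |
| Infection, RR 0.87 at 20% | 80% | 77.6% | 75.5% |
| Serious disease, RR 0.65 at 3% | 80% | 78.7% | 76.6% |

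The two 80% infection cells are already below 80% at 6650 because of rounding: the exact detectable RRs are 0.897 and 0.866, printed as 0.90 and 0.87.

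**Step 5: detectable RRs for 80% power at 6317.5.** Infection 0.894 at 30% and 0.863 at 20%; serious disease 0.636 at 3% control risk (0.645 at 6650).

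**The case against.** **6650 may already be net of the loss.** The footnote calls it the number with evaluable results and points to the text for its rationale, and 7000 × 0.95 is exactly 6650. This cannot be excluded. But section 9.4.4 gives no 7000; it calls 6650 the number remaining in March 2020 and calls the 5% additional. On that reading the table stands and the March 2020 figure is wrong, so the section still needs correcting.

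**The table reports effect sizes, not powers.** Power is the input and RR the output, shown to two decimals. Putting a rounded RR back in will move the power, and it can move up as well as down: the text's 30% versus 26% gives 95.3% at 6650 and 94.3% after the loss, both above the stated 90%. This stands. Two-decimal rounding is not an error in itself, and after the loss the RR for 90% power at 30% positivity is 0.878, which still prints as 0.88.

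**The serious-disease figure depends on the denominator.** If only antibody positives were compared, the headline would be 81.1% before and 79.1% after the loss. All randomised is used here because it reproduces the table. In addition, section 9.6.4 analyses COVID-19 diagnoses and serious disease by incidence rate ratio with person-time from January 2020, so participants lost later still contribute. Removing a full 5% is then somewhat pessimistic for that endpoint.

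**Nothing in the design depends on it.** Participants were already enrolled, and the table's 15% to 30% span of positivity is a larger uncertainty than 5% of the sample. This also stands, and it limits the importance of the point.

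**Conclusion.** The inconsistency is real: the text claims a 5% allowance that neither its counts nor its table contains. If 6650 is the March 2020 headcount, as the text says, the counts are about 5% too high. The omission alone costs roughly 2 points of power or less: 80% becomes 78.0%, 85% becomes 83.2% and 90% becomes 88.5%.

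A reader might infer that several stated powers are really 75% to 77%. The documents do not support that as a consequence of the missing deduction. Those values arise only in the 80% row, only when printed RRs are put back into the formula so that rounding adds to the loss, and for serious disease only with the all-randomised denominator. Nor do the documents establish beyond doubt that 6318 is the right evaluable number.

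The figures assume a pooled two-proportion z test, two-sided 5%, 1:1 allocation and 6650 as the number before loss. The consequence is small and limited to the secondary COVID-19 objectives. The 288-event calculation for primary MACE is unaffected.

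**What to change.** State in section 9.4.4 whether 6650 is before or after the 5% loss.

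- **If before, as the text reads:** restate about 6318 evaluable, 1895 cases, 4422 controls and 190 hospitalisations, and recompute Table 9.4.4-1 and its footnote on that number. For 80% power the entries would include infection RR 0.894 at 30% and 0.863 at 20%, and serious-disease RR 0.636 at 3% control risk.
- **If after:** correct the number said to have remained in follow-up in March 2020, and leave the table.

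In either case, give the RRs to three decimals and name the serious-disease denominator, so that each cell can be checked against its stated power. The cost is one paragraph and at most one table, with slightly less favourable figures if the loss is deducted. Nothing in the conduct of the trial changes.

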**Table 9.4.4-1: Detectable Effect Sizes for Antibody Positivity Rates of 15%-30% and Power of 80%-90%**

Power		Proportion of Participants COVID-19 Antibody Positive (Control)			
		30%	20%	15%	
Precision to estimate infection risk	-	$\pm 0.012\%$	$\pm 0.0135\%$	$\pm 0.015\%$	
Detectable risk reduction with given power	90%	12% ( $RR=0.88$ )	15% ( $RR=0.85$ )	18% ( $RR=0.82$ )	
	85%	11% ( $RR=0.89$ )	14% ( $RR=0.86$ )	17% ( $RR=0.83$ )	
	80%	10% ( $RR=0.90$ )	13% ( $RR=0.87$ )	16% ( $RR=0.84$ )	
		Proportion of COVID-19 antibody positives experiencing serious disease			
		10%	20%	10%	20%

Detectable risk reduction with given power	90%	40% (0.60)	29% (0.71)	48% (0.52)	35% (0.65)	55% (0.45)	40% (0.60)
	85%	38% (0.62)	27% (0.73)	45% (0.55)	33% (0.67)	51% (0.49)	38% (0.62)
	80%	35% (0.65)	25% (0.75)	43% (0.57)	31% (0.69)	48% (0.52)	35% (0.65)

*\* Assumes sample size of 6650 with evaluable COVID-19 antibody results equally distributed between pitavastatin and placebo groups (see text for rationale for this number).*

## 9.5 Monitoring

The following is a summary of the data and safety monitoring plan for REPRIEVE (A5332). Prior to enrollment of the first participant, a detailed study monitoring and analysis plan document will be prepared that will more fully describe these data monitoring aspects including timelines and responsibilities for preparation.

Summaries of accrual rates, deaths, SAEs, and targeted AEs across regimens as well as study conduct (in terms of off-study rates, and completeness of study visits) will be reviewed on a regular basis by the protocol core team with all data pooled across study arms. Further, in line with the NHLBI Accrual Guidelines of observed against target accrual benchmarks will be reviewed by NHLBI program staff at a minimum of 25%, 50%, and 75% of the anticipated accrual period. Additional accrual reporting to NHLBI will be provided as requested. The timing and anticipated enrollment by 25%, 50%, and 75% of the accrual period are shown in [Table 9.5-1](#).

Table 9.5-1: Accrual Benchmarks at 25%, 50%, and 75% of the Accrual Period

Recruitment Period	Time after First Patient Enrollment	Projected Accrual
25%	7.5 months	767
50%	15 months	2740
75%	22.5 months	4635

The study will undergo at least annual review by an NIH appointed DSMB for study conduct, continued feasibility, safety, and efficacy.

Unless otherwise noted, the unblinded REPRIEVE (A5332) statisticians will be responsible for all data analysis and report preparation to the DSMB. The DSMB will be appointed by NHLBI in consultation with DAIDS. For each review, the statisticians will prepare 3 summary reports: 1) a closed report containing all information broken down by masked treatment group distributed only to the DSMB; 2) a report for REPRIEVE (A5332) PIs and the NIH (NHLBI and DAIDS) team that will include MACE endpoint information pooled over both treatment groups; and 3) an open administrative report with administrative and safety information pooled over treatment groups. Specific contents of reports will be discussed with the DSMB prior to the first review. An outline of the focus of each review is provided in Table 9.5-2 below; further details and rationale are provided in the text below. These details are provided in broader detail in the Statistical Analysis Plan.

Table 9.5-2: Overview of DSMB Monitoring Focus

Focus		Timeframe
Feasibility and conduct	Site activation, enrollment, data and visit completeness, rates of loss to follow-up and cross-over	At all interim reviews occurring at least annually
Safety	Rates of adverse events by treatment group	At all interim reviews occurring at least annually
Event rate evaluation	Pooled rates of events observed to date; predicted confidence interval of the pooled event rate under a range of realistic scenarios*	At all interim reviews occurring at least annually
Formal efficacy and futility review	Treatment group comparison for the primary endpoint utilizing group sequential methods	Interim looks for efficacy are planned at approximately 50% and 75% statistical information, or as otherwise recommended** .

\* To be conducted if the pooled rate falls below a specified target (see Statistical Analysis Plan).  
\*\* Statistical information for the MACE endpoint is based on the total number of expected MACE endpoints (see Statistical Analysis Plan for more details).

The first feasibility review will occur approximately one year after the accrual of the first participant with a focus on site activation and patient accrual and retention as well as rates of treatment crossover. Benchmarks for these aspects are provided in detail in the Statistical Analysis Plan that will be reviewed and agreed upon by the DSMB. In addition to these aspects, pooled rates of events observed to date will be reviewed by the DSMB at all reviews to evaluate the adequacy of the sample size assumptions. Given the expected rate of accumulation of events it is anticipated that sufficient events will have been accrued to the study by the time of reviews occurring 2-2.5 years after enrollment of the first participant to allow reasonable determination of whether the underlying rate of event accumulation is inconsistent with observing the required total number of events to achieve 90% power to detect a HR of 0.70 at the study conclusion. This is illustrated by the anticipated rate of event accumulation dependent on the interim review timing shown in Table 9.5-3.

Table 9.5-3: Anticipated Data and Event Accumulation Dependent of Interim Review Timing

Timing of review (y)	Number of participants enrolled*	Accumulated person years of follow-up*	Expected total accumulation of events under given event rate in control group (all cases assume the target HR of 0.7)		
			15/1000	12/1000	10/1000
1	508	127	2	1	1
1.5	1944	972	12	10	7
2	3609	707	34	28	21
2.5	5414	5685	72	58	43
3	6500	8125	103	82	62
3.5	6500	11375	143	115	86

\*Assumes data freeze 4 months prior to DSMB review and enrollment benchmarks agreed with NHLBI.

The event rate evaluation will be performed by a blinded REPRIEVE (A5332) statistician. In the event that the observed number of events falls short of the predetermined benchmarks providing in the statistical analysis plan, a predicted confidence interval analysis will be performed for the total expected number of MACE at trial conclusion based on accumulated data to date and a range of scenarios for accumulation of future data. These will include but not be limited to continued accumulation as observed and, under the target effect size of  $HR = 0.70$ , control MACE rate of 12/1000 PY and 15/1000 PY. Unless otherwise requested by the DSMB, these assessments along with recommendations for any study design changes will be presented only in the closed study report, and thus available only to members of the DSMB. Release of the information to the REPRIEVE (A5332) Executive Committee will be at the discretion of the DSMB.

If any of these assessments suggest that the anticipated total number of events appear substantially smaller than the rate assumed for sample size considerations or if accrual is below anticipated, consideration will be given to modifying the design of the study. Such considerations may include (but will not be limited to) extending the study duration, increasing the target sample size, and broadening the study entry criteria to include individuals with low/moderate traditional CVD risk who are willing to be randomized to statin therapy or placebo, for example, participants who have an ASCVD risk score of  $\geq 7.5\%$ .

Unless there are emerging feasibility or safety concerns, guidelines for stopping or modifying the trial will be guided by formal efficacy review to occur once sample size adequacy for the study has been established. **A total of four interim looks were planned originally: at 20% (if requested by DSMB), 40%, 60%, and 80% information. Per recommendation of NHLBI, endorsed by the DSMB at the December 2019 meeting, the timing of interim looks was changed to 50% and 75% information to allow for the best possible decision about extending study follow-up duration. Inference at each interim efficacy review will be guided by a Lan-DeMets implementation of the O'Brien-Fleming sequential stopping boundary with information measured on the cumulative number of primary MACE endpoints at the time of the review.** This implementation permits early stopping only for very strong positive or negative effects and maintains most of the nominal power for **when the majority of information has accrued**. For example, under the hypothesized effect size ( $HR=0.7$ ), the cumulative probability that the interim result will cross a boundary at 50% information is 33% compared to a 78% probability at 75% information. The ultimate recommendation of all reviews—irrespective of whether boundary p-values have been achieved—will be at the discretion of the DSMB.

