9.2.3.2 Time to heart failure

9.3 Randomization and Stratification

At study entry, participants will be assigned with equal probability to one of the two treatment arms. Randomization will use permuted blocks with stratification by sex (male/female) and screening CD4+ T-cell counts ( $\leq 500$  vs.  $> 500$  cells/mm $^3$ ). Additionally, to ensure balanced treatment allocation for the Mechanistic Substudy of REPRIEVE (A5333s), randomization will also be stratified by whether or not a participant has elected to participate in the mechanistic substudy (yes/no). Total enrollment of individuals with low cardiovascular risk (10-year ASCVD risk score  $< 5.0\%$ ) was capped at approximately 4200 participants, to ensure that the final study population reflects the targeted low-to-moderate risk population. It is anticipated that the study will take 48 months to fully enroll.

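### The stated chances of crossing the interim boundary (33% at 50% information, 78% at 75%) do not fit the 288-event design, which gives about 21% and 61%.

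*Protocol*

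**What the plan says.** Section 9.4.2 sets the current design: "a total of 288 primary MACE endpoints are needed to ensure that the study will have 85% power to detect a hazard ratio of 0.7". Section 9.1 makes the same 288 events the closure target, unless the DSMB recommends closure on other grounds. Section 9.5 says that "the timing of interim looks was changed to 50% and 75% information", in order to inform the decision on extending follow-up. Inference at each look uses a "Lan-DeMets implementation of the O'Brien-Fleming sequential stopping boundary with information measured on the cumulative number of primary MACE endpoints".

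The same paragraph then gives one worked illustration under HR 0.7: "the cumulative probability that the interim result will cross a boundary at 50% information is 33% compared to a 78% probability at 75% information". It does not give the event total behind these two figures.

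**The concern.** The sentence names the hazard ratio, the look times and the boundary, so a reader will take the two probabilities as properties of the 288-event plan. A design with 85% power in total cannot easily have spent 78 points of it by the 75% look under an O'Brien-Fleming-type boundary, which holds most of its power back for the end.

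What is at stake is expectation. The looks were moved to help decide how long to follow participants. A planner who accepts 78% will think that a trial with the hoped-for effect goes past 75% information only about one time in five. Such a planner will under-plan for the full 288 events and will read a non-crossing at 216 events as stronger evidence against HR 0.70 than it is.

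**Working it through.** **Inputs, all from the protocol**

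- Events at full information: 288 (9.4.2; also 9.1).
- Effect: HR 0.70 (9.4.2, and the illustration in 9.5).
- Allocation: "participants will be assigned with equal probability to one of the two treatment arms" (9.3).
- Error rate: "Statistical comparisons will be performed using two-sided significance tests with a 5% Type I error" (9.6.1), so 0.025 per side.
- Looks at 50% and 75% of events (144 and 216), then the final analysis; Lan-DeMets O'Brien-Fleming spending on the event count (9.5).

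**Boundaries.** Cumulative error spent per side at information fraction t is 2 − 2Φ(z/√t), with z = Φ⁻¹(1 − 0.025/2). This gives 0.00153 at t = 0.5, 0.00965 at 0.75 and 0.025 at 1. Solving look by look gives Z = 2.963, 2.359 and 2.014.

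**Drift.** Expected Z at full information = ln(1/0.7) × √288 / 2 = 3.026. Expected Z is 3.026 × √0.5 = 2.140 at the first look and 3.026 × √0.75 = 2.621 at the second.

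**Check against the plan's own power.** The cumulative crossing probability by the final look is 85.0%. With this boundary and these looks, 288 is the smallest event total that reaches 85% (287 gives 84.9%). The design therefore reproduces the power in 9.4.2.

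**Crossing probabilities from the same calculation**

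- First look: 1 − Φ(2.963 − 2.140) = 1 − Φ(0.823) = 20.5%.
- By the second look: 1 − P(Z₁ < 2.963 and Z₂ < 2.359), bivariate normal with means 2.140 and 2.621 and correlation √(0.5/0.75) = 0.816. This is 1 − 0.393 = 60.7%.

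Two million simulated trials gave the same 20.5% and 60.7%.

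| Quantity | Stated | Recomputed | Gap |
|---|---|---|---|
| Crossed at 50% | 33% | 20.5% | 12.5 points |
| Crossed by 75% | 78% | 60.7% | 17.3 points |
| Not crossed by 75% | 22% (implied) | 39.3% | 17.3 points |

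**Other conventions (50% / 75%), at 288 events and HR 0.70**

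- Freedman drift: 19.9% / 59.6%.
- Two-sided 0.05 spending function halved per side: 26.4% / 63.3%.
- Classical O'Brien-Fleming: 24.4% / 62.6%.
- Extra looks at 20% and 40%: 20.2% / 60.7%.
- One-sided 5%, contrary to 9.6.1: 34.5% / 73.3%.
- Pocock: 44.1% / 66.0%.

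None gives the stated pair.

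**What would give it.** A crossing probability of 33% at the first look needs about 400 events, and 78% by the second needs about 409, at HR 0.70 (overall power 94% to 95%). With 288 events, the pair needs a hazard ratio of about 0.654 to 0.657. The original design does not fit either: 6500 participants, 2.5 years of accrual, 6 years in total, 15/1000 PY and 5% annual loss give about 338 expected events and, with looks at 50% and 75%, 26% and 69%.

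**The case against.** Three points can be made for the text.

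**The figures may be a correct calculation on another basis.** Take the intermediate design: 7500 participants and 84 months (9.1), 48 months of accrual (9.3), 15/1000 PY and 5% annual loss (9.4.1), HR 0.70, and uniform accrual as an assumption. Expected events are then about 406, and the crossing probabilities are 33.7% and 77.7%, within a point of the stated pair. This is a plausible source, although the documents do not confirm it. It explains the numbers without rescuing them, because the protocol now ties the trial to 288 events and presents the pair with no other basis.

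**A futility boundary might be counted.** Table 9.5-2 describes the review as covering both efficacy and futility, and the sentence refers to crossing a boundary without saying which. No futility rule appears in the documents supplied; the SAP supplied covers only the A5333s substudy, and the main-trial SAP was not available. An assumed O'Brien-Fleming-type futility rule at 288 events gives 24.7% / 70.3%, and an assumed Pocock-type one about 30% / 73%. A binding Pocock-type rule sized for 85% power does reach 33% / 78%, but at about 318 events, not 288. The timeframe column of the same table speaks of interim looks for efficacy.

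**The consequence is small.** This stands in large part. The sentence is an example, and its qualitative message, that power is held for later looks, survives with the right numbers. DSMB recommendations remain discretionary, and nothing shows that anyone has planned from the 33% and 78%. It is also fair that 288 need not have come from a group-sequential calculation: fixed-sample formulas give 283 (Schoenfeld) and 289 (Freedman). The crossing probabilities follow from 288 events however that total was reached.

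**Conclusion.** The sentence is wrong as written. For the plan's 288 events at HR 0.70, the chance of crossing the efficacy boundary is 20.5% at 50% information and 60.7% cumulatively by 75%, against 33% and 78% stated. The chance of continuing past 75% information is 39%, not 22%. This rests on the protocol's own inputs and on reading the boundary as the efficacy boundary that section 9.5 describes. The boundaries, the error rate, the 288-event target and the 85% power are unaffected. The error is material to what readers expect of the looks, and modest in its effect on the conduct of the trial.

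**What to change.** Replace the two figures in section 9.5 with about 21% at 50% information and about 61% cumulatively by 75%, and state the basis beside them: 288 events, HR 0.70, overall power 85%. Say that the probabilities refer to the efficacy boundary. If the main-trial SAP contains a formal futility boundary that was meant to be counted, give its crossing probabilities separately. Any planning of extended follow-up should use a 39% chance of going on past 75% information under HR 0.70. If the sponsor wishes to keep 33% and 78% for the record, the event total and effect size behind them must be named and marked as not the current design. The cost is one sentence and a less favourable stated figure.
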